4.6 Knowledge-based questions

The following knowledge-based questions will be asked to the adult participant who performed the test. Participants will be advised they should refer to the materials available when answering the questions.

Table 9 -	Knowledge-based	questions
-----------	-----------------	-----------

Question number	Knowledge based question	Acceptance criteria
1	How often is it recommended that you do this test?	Depends on circumstances and current national or local guidelines

2	Where can you find information on what to do if you have coronavirus symptoms or have a positive test for coronavirus?	NHS guidance online. nhs.uk/conditions/coronavirus- COVID-19
3	What are you advised to do if you have coronavirus symptoms and are deteriorating, or your symptoms last longer than a week?	User indicates one or all of following: Go online to: NHS 111 online coronavirus service, 111.nhs.uk . If you do not have internet access, call NHS 111. For a medical emergency dial 999.
4	What should you do if there is something missing or damaged in the kit?	User indicates one or all of the following: Do not use it. Call, using the numbers below, and ask for a new kit: - England, Wales and Northern Ireland: 119 (free from mobiles and landlines) - Scotland: [name] (charged at your standard network rate)
5	If while using the kit something breaks what in addition should you do?	Report the problem via the Coronavirus Yellow Card website, coronavirus- yellowcard.mhra.gov.uk
6	How should you ensure your hands are clean before you start using the test?	Wash your hands thoroughly for 20 seconds, using soap and warm water OR use hand sanitiser
7	Once you have opened the test kit when should the test be started	Within 30 minutes
8	What should you do if you touch the swab with your gum?	Get a new swab.
9	How long should you wait before reading the test result?	30 minutes.
10	What should you do if you leave the test to develop but get distracted and only come back to looking at the test after 1 hour?	If you leave the test to develop for longer than 35 minutes this will make the test result invalid.
11	What does this test result indicate:	Two lines – even faint lines – indicate the test is positive.

12	What does this test result indicate:	The test is invalid
13	What does this test result indicate:	This indicates the test is negative.
14	How should you report a positive result?	Answers can include: Report online www.gov.uk/covid19-self-test- help/ Or scan this QR code with your smart phone to open the reporting website Report by telephone England, Wales and Northern Ireland: 119 (free from mobiles and landlines) Scotland: [name] (charged at your standard network rate)
15	What should you do if a child's symptoms are worsening?	Visit NHS online www.111.nhs.uk or call 111
16	How should the test kit be disposed of after using?	Put all of the used test kit contents in the waste bag provided and place in your household waste

4.7 Root cause investigation

Once participants have completed the simulated use, the moderator will conduct follow-up questioning to investigate the root cause of any use errors, use difficulties, or close calls for the simulated use sessions and knowledge-based/scenario-based questions.

4.8 Suggested improvements

Following root cause investigation, the participant will be asked for their views on what could be improved with the IFU and testing process.

4.9 Debrief

After the interview the moderator will thank the respondent and conclude the interview. The respondent will be offered the chance to ask any questions and offer any further improvements to the packaging and IFU.

4.10 Data Collection

Study personnel will include the study moderator, who will facilitate the study and interview the participant, and a study observer, who will capture data. The study observer will capture notes in electronic form. A video recording will be taken of each session.

Specifically, the following data will be collected during each session:

- Participants' demographic background information
- Task performance for each task (successes, use errors, close calls and use difficulties)
- Participant-reported root causes for use errors, close calls and use difficulties
- Participants' comments (paraphrased)
- Participants' responses to subjective and open-ended questioning posed during the post-task and post-study interviews
- Moderator and observer observations.

The definitions used to categorise task performance are located in Table 4.

Any previously unanticipated use errors will be observed and recorded and included in the follow-up interviews with participants. In the unlikely event of system failures, these will be noted in the data collection and sequence of events leading up to the device failure will be described in the report.

4.11 Analyses

After all sessions are completed, the collected data will be analysed to determine if the task performance was a success, use error, close call, or use difficulty, as per the criteria defined in Table 10. Root cause analysis will be conducted on all tasks where use errors, close calls, and use difficulties were present. This analysis will draw upon study video data, participant responses from post-task interviews, and expert review of the use problem.

Outcome	Definition	Root Cause Investigation Required?	Method of Scoring Data
Success	Participant performs the task correctly on the initial attempt without assistance	No	Success Close Call Use Error N/A

Table	10 -	Scoring	definitions
-------	------	---------	-------------

Outcome	Definition	Root Cause Investigation Required?	Method of Scoring Data
Close Call	 Any instance in which a participant makes a use error e.g. by attempting to undertake an action without accurate reference to the IFU, but then retries resulting in a successful completion of a user step. This outcome also considers: The user verbally expresses frustration or facial expressions and body postures indicate frustration when using the device; The user re-reads the same section of the IFU during a task, in an attempt to comprehend a sequence of steps use The user is able to accomplish a task or step, but experiences frustration or discomfort in the process of doing so. 	Yes	Success Close Call Use Error N/A
Use Error	 Any action or lack of action while using the packaging that leads to a different result than that intended by the manufacturer or expected by the user, including: A participant's inability to complete a task; A deviation from the IFU that leads to a device response that is different than intended or expected by the participant; An instance where the participant requires assistance from study personnel to advance through tasks. The following will not be considered use errors: A malfunction of the packaging that causes an unexpected result. 	Yes	Success Close Call Use Error N/A
Use Difficulty	 Any observed difficulty on the part of the user while performing the test, which does not result in a use error, but points to an underlying usability concern with the IFU or test kit, Examples include (but are not limited to): The user verbally expresses frustration or facial expressions and body postures indicate frustration when using the packaging; The user re-reads the same section of the IFU during a task, in an attempt to comprehend a sequence of steps The user is able to apply the required amount of force or dexterity to accomplish a task or step with the kit, but experiences frustration or discomfort in the process of doing so. 	Yes	Yes/No This metric is collected in addition to the observational score of Success/Close Call/Use Error

Outcome	Definition	Root Cause Investigation Required?	Method of Scoring Data
N/A	If a task cannot be completed for a reason out of the control of the participant, the task should be scored as N/A. While root cause investigation is not required, notes need to be collected to indicate the reason for scoring N/A. Some examples include: • Packaging failure	No	Success Close Call Use Error N/A

5 Study considerations

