2.2 Objective

The primary objective of this study is to validate that the LFD kit is safe and effective to use by the intended user population in the intended use environment.

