2.4 Background

The LFD in-home test kit is currently being developed for distribution to the general public within the United Kingdom.

A key feature in the successful undertaking of the test is the ability for users to understand the steps of use and to understand the general information contained within the IFU.

The DHSC would therefore like to determine whether the IFU design enables safe and accurate test results to be achieved.

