4.4 Simulated use adult and adolescents

Participants will be asked to open the pack and to follow the steps of use presented to them.

The moderator will observe the participant complete the steps of use. To ensure the task is representative of a real-use scenario, the moderator will not interact with the participant during this task and will not offer help to the participant. The moderator will only verbally interject if the participant gives up on the task, or if the moderator foresees a dangerous scenario developing. A list of tasks and their success/use-error criteria are found in the discussion guide Appendix 6 and section 4.1.1

During the simulated use participants are expected to undertake all steps as described in the IFU to perform a self-test using the LFD test kit.

This task begins with all the study components in their unopened form on the table and ends with the participant indicating that they have done everything they would do at home to perform the test.

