Use step 13 Gently squeeze the extraction tube to place 2 drops of liquid onto the specimen well on the test strip.	Participant tips the extraction tube to place 2 drops of liquid onto the test strip sample well.
Use step 14 Place the test strip on a flat and level surface Check the time or set a timer if you have one. Wait 30 minutes to read your result.	Participant places test strip on a flat surface Participant checks the time or sets timer for 30 minutes and leaves the test strip without touching it. After 30 minutes the participant reads the result.

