WHILE WAITING FOR THE TEST RESULTS PROCEED WITH 6.5

NOTE TO MODERATOR: RECORD CURRENT TIME AND SET A TIMER FOR 30 MINUTES.

6.4 **CAREGIVER** Simulated use and Root Cause (40 mins)

The test-kit that you are going to use today is detects the presence of COVID-19. You would use this test-kit on yourself or someone you care for, and it would be posted to your home as part of the UK Government's Test and Trace scheme.

I now want you to imagine that you have been sent the test kit and it's time to perform the test on your child/family member. Remember this is a real test which is going to give you a real result, so please do everything you would do if I weren't here today. Once you have finished let me know and I will ask you some questions.

When giving yourself the test, please refer to the instructions provided to you in the kit.

Do you have any questions before we start?

You may now proceed to do the test.

REFERRED TO IFU? YES / NO

Use Step/Acceptance criteria	Use Error	Use Difficulty	Close Call	Pass	Comments
Clear, clean and dry a flat surface to place the home test kit on.					
Wash your hands thoroughly for 20 seconds, using soap and warm water, or hand sanitiser.					
Take the test kit out of the foil packaging and place it onto the cleaned flat surface.					
Setup your test					
Use Step 1 Carefully twist or snap open the sachet					
Use Step 2 Pour all of the fluid from the sachet into the extraction tube.					

Use Step/Acceptance criteria	Use Error	Use Difficulty	Close Call	Pass	Comments
Use Step 3 Place the filled tube in a cup or container to avoid spilling it while you use the swab					
Use Step 4 Check the swab in the sealed wrapper in front of you					
Use step 5 (Not required for non self test) Gently blow your nose into a tissue.					
Use step 6 Wash and dry your hands again (or use sanitiser if this is available).					
Use Step 7 Open the swab package and gently take out the swab.					
Take your swab sample					
Use step 8 (child/dependant) Ask the child to open their mouth wide, then rub the fabric tip of the swab over both tonsils (or where they would have been). Do this with firm contact 4 times on each side. Carefully remove the swab. If you cannot swab the tonsils, you can swab both nostrils.					

Use Step/Acceptance criteria	Use Error	Use Difficulty	Close Call	Pass	Comments
Use Step 9 (child/dependent)					
Put the fabric tip of the same swab gently into one of their nostrils until you feel some resistance.					

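### Section 4.11 works task by task and no outcome is defined per test performed, so task tallies cannot show how many tests were free of a result-relevant use error

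*Protocol*

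**What the plan says.** The primary objective in section 2.2 is to "validate that the LFD kit is safe and effective to use by the intended user population". Section 2.4 gives the sponsor's question, which is to "determine whether the IFU design enables safe and accurate test results to be achieved". Both concern the whole test. Section 4.4 treats the steps as one sequence: "participants are expected to undertake all steps as described in the IFU to perform a self-test using the LFD test kit".

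The data and analysis sections work at a different level. Among the data to be collected, section 4.10 lists "Task performance for each task (successes, use errors, close calls and use difficulties". Section 4.11 states that "the collected data will be analysed to determine if the task performance was a success, use error, close call, or use difficulty", using the definitions in Table 10, and continues: "Root cause analysis will be conducted on all tasks where use errors, close calls, and use difficulties were present". The discussion guide (6.3.1 and 6.4) has one scoring row per step. Section 6.7 of the guide scores the reading of the participant's own strip as one further item, correct or incorrect.

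No section defines an outcome per participant or per test, and none says which steps could affect the result.

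**The concern.** A home test is a chain. An error in sampling, extracting, dropping, timing or reading may compromise the result, and a success in another row does not undo it. Whether a kit can be used effectively therefore depends on how many people get through the steps that matter without an error.

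Classifying tasks one at a time does not give that number. Two data sets with identical counts of use errors at every step can differ widely in the number of tests affected, depending on whether the same participants err repeatedly or different participants err at different steps.

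Section 6.7 does not fill the gap. It asks only whether the strip was interpreted correctly, so a correctly read strip from a badly taken sample counts as a success.

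What is at stake is the step from task scores to the conclusion on 2.2. As written, the study could report every task in detail and still not state how many of the 60 tests were carried out properly.

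**Working it through.** **Inputs from the protocol**
- Sample size: 4 groups × 15 = 60 (section 3.6, Table 4). This agrees with the stated total.
- Rows in Table 7: 3 preparation rows + Use Steps 1 to 14 = 17. The last begins "Use step 14 Place the test strip on a flat and level surface".
- Caregiver groups: Table 8 repeats Steps 1 to 7, but section 6.4 of the discussion guide has "Use step 5 (Not required for non self test". The count for these 30 participants is thus 17 or 16, and the two places must be reconciled.
- Step 4 is not scored in its own right. Table 7 deems it a success if the swab orientation is correct in Step 8.

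**Inputs that are assumptions**
- Number of result-relevant items: 10. The protocol does not rank steps by consequence. One candidate list is Step 2, Steps 7 to 14 and the reading of the own strip: 1 + 8 + 1 = 10.
- Participants who err on each item: 1, 2 or 3 of 60. The protocol gives no expected rate and no threshold.

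**Formulas.** Let e participants of 60 err on each of k items.
- Fewest tests with an error: e (the same people err every time).
- Most tests with an error: min(60, k × e) (different people each time).
- Under independence: 60 × [1 − (1 − e/60)^k].

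The first two need no assumption about how errors are related.

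**Results: tests out of 60 with at least one error**

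| Errors per item | Success per item | 10 items: range | 10 items: independent | 17 rows: range | 17 rows: independent |
|---|---|---|---|---|---|
| 1 of 60 | 98.3% | 1 to 10 | 9.3 | 1 to 17 | 14.9 |
| 2 of 60 | 96.7% | 2 to 20 | 17.3 | 2 to 34 | 26.3 |
| 3 of 60 | 95.0% | 3 to 30 | 24.1 | 3 to 51 | 34.9 |

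For e = 3 and k = 10: 0.95^10 = 0.599, and 60 × (1 − 0.599) = 24.1. The upper limit is 10 × 3 = 30.

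**Sensitivity to the row count (e = 3)**
- 16 rows, without Step 5: upper limit 16 × 3 = 48; independent value 60 × (1 − 0.95^16) = 33.6.
- 15 rows, also without Step 4: upper limit 15 × 3 = 45; independent value 60 × (1 − 0.95^15) = 32.2.

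The disputed rows move the figures slightly. Under every count the task tallies alone leave a wide range.

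**The case against.** The strongest reply is that the choice of summary tables belongs in a statistical analysis plan or the study report. Section 4.11 says how observations are classified and which are investigated. It prescribes no tables, and it does not exclude a count per participant. The unique codes in section 3.8 make such a count possible at any time. This stands in part: the protocol makes no false statement here, and the point is an improvement, not the correction of an error. But the protocol has its own analysis section, and the only unit it uses is the task, while its objective is stated for the whole test. That mismatch is in the protocol itself.

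A second reply is that 4.11 never says step success rates will be calculated or will decide the conclusion. A reader might infer that the verdict of safe and effective will rest on high step rates. The text does not support that. What it commits to is root cause analysis of every task with a problem, so a single error by a single participant triggers an investigation and is not hidden. This stands in full. Root cause analysis explains errors, however; it does not count the tests affected.

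A reader might also infer that a large share of tests will contain an error that spoils the result. The documents do not show this. Every rate above is assumed, the 17 rows include cleaning the surface and blowing the nose, and if errors cluster in the same people the number of tests affected falls to the per-item count.

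Finally, the choice of items can be disputed. Restricting the list to Steps 7 to 13, for example, would leave out Step 2 (transferring all the fluid) and Step 14 (timing), and would include the disposal of the swab in Step 11. The list must therefore be agreed and not taken for granted.

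**Conclusion.** The point holds as a gap between the unit of analysis and the objective. Performance is scored and investigated by task, no outcome per test is defined, and task tallies alone cannot supply one. With 3 of 60 participants erring on each of 10 items, the same tallies are compatible with 3 to 30 affected tests, about 24 under independence; over all 17 rows of Table 7 the range is 3 to 51.

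That the tallies cannot separate these cases follows from the bounds and depends on no particular error rate. The size of the range does depend on the assumed rate and number of items, and independence is only a reference case. The figures do not predict how many tests will go wrong. This is a cheap improvement that lets the study answer its own question; it does not make the data unusable.

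**What to change.** Before the sessions:

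1. List the result-relevant items. A starting point is Step 2, Steps 7 to 14 without the disposal part of Step 11, and the reading of the own strip (6.7). The sponsor should confirm the list.
2. State how a row scored N/A is counted, and reconcile Table 8 with the caregiver guide on Step 5 so that the set of scored rows is fixed.

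Add to section 4.11:

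3. The number of participants with no Use Error on any listed item, and the number with none on any scored row, for each user group (n = 15) and overall (n = 60), with an exact confidence interval. Show Close Calls separately.
4. A statement that these counts will be reported beside the task table and the root cause analysis when concluding on 2.2. It should add that the study has no reference result, so the counts show correct performance and not the accuracy of results raised in 2.4.

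The cost is one extra table. No further data, participants or session time are needed, and root cause analysis by task stays as it is. The drawback is a figure that may look less favourable than the task-level results, with wide intervals in groups of 15. Even 15 of 15 without error has an exact two-sided 95% lower limit of 0.025^(1/15) = 78%.

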Use step 8 Holding the swab between your fingers, open your mouth wide and rub the fabric tip of the swab over both tonsils (or where they would have been). Do this with firm contact 4 times on each side (use a mirror to help you do this). Carefully remove the swab from the back of your throat.	Participant rubs the fabric/soft tip of swab over both tonsils (or where they would be if they have been removed) with at least 4 observable directional movements.
	Participant removes the swab from their throat without touching any part of their mouth at this stage (not touching tongue, teeth, cheeks, gums etc)

Use step 9 Put the same swab gently into one nostril until you feel a slight resistance (about 2.5cm up your nose). Roll the swab firmly around the inside of the nostril, making 10 complete circles.	Participant puts the same swab fabric/soft tip into one nostril about 2.5 cm up nostril. Participant rolls the swab around the circumference of their nostril in full circles at least 10 times. Participant then places the same swab fabric/ soft tip into the other nostril about 2.5 cm up nostril. Participant rolls the swab around the circumference of
	the other nostril in full circles at least 10 times.
Process the swab sample	
Use step 10 Remove the extraction tube from the cup and place the fabric tip of the swab into the extraction tube so it is in the fluid. Press the tip against the edge of the extraction tube with force, while rotating it around the tube for 15 seconds.	Participant places the fabric/soft tip of the swab into the extraction tube. Participant presses the fabric/soft tip of the swab against the side of the extraction tube with force while rotating the swab around the extraction tube for 15 seconds.
Use step 11 Pinch the tube as you remove the swab to make sure that all the fluid is removed from the soft tip of the swab. Place the swab in the plastic waste bag provided.	Participant takes out the swab whilst squeezing the extraction tube and fabric/soft tip of the swab (to squeeze as much fluid out of swab as possible). Participant puts the swab into a plastic bag and disposes of it into their household rubbish.
Use step 12 Press the nozzle cap tightly on to the extraction tube to avoid any leaks	Participant presses the nozzle cap tightly onto the extraction tube (to avoid leaks).

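### Table 10 defines a Use Error by its consequence, Tables 7 and 8 by observed technique, so an uncorrected sampling deviation with an ordinary negative strip has no clear score

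*Protocol*

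**What the plan says.** Section 4.11 makes Table 10 the rule for deciding whether a task was a success, use error, close call or use difficulty. Its rows rest on different principles.

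- **Success** is about process: "Participant performs the task correctly on the initial attempt without assistance".
- **Close Call** needs a recovery. The participant errs, "but then retries resulting in a successful completion of a user step".
- **Use Error** is about consequence: "Any action or lack of action while using the packaging that leads to a different result than that intended by the manufacturer". A departure from what the user expected counts as well. Three examples follow. The first is "A participant's inability to complete a task". The second, the only one about departing from the IFU, is "A deviation from the IFU that leads to a device response that is different than intended or expected by the participant". The third is "An instance where the participant requires assistance from study personnel to advance through tasks".
- **N/A** is kept for causes outside the participant's control.
- **Use Difficulty** is a yes/no flag added to the score, not an alternative to it.

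Tables 7 and 8 (sections 4.4.1 and 4.5) give each step an observable acceptance criterion. For nasal sampling in Table 7 it is "Participant rolls the swab around the circumference of their nostril in full circles at least 10 times". For extraction the swab must be pressed "with force while rotating the swab around the extraction tube for 15 seconds". Section 4.4 describes the listed task criteria as the ones that separate success from use error. Table 10 does not mention them.

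**The concern.** Steps 8 to 11 cover throat swabbing, nasal swabbing, extraction and removal of the swab. The only thing the device shows in response to these steps is the strip, read 30 minutes later. If the tested person does not carry the virus, the strip is expected to be negative whether the swabbing was thorough or cursory. A rule that looks for an unexpected device response does not pick up that kind of deviation, whereas a rule that looks at technique does.

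Section 2.4 says the sponsor wants to know whether the IFU design leads to safe and accurate results, and poor sampling bears directly on that. If raters are free to apply either rule, the use-error counts for these steps depend partly on which page they follow. Section 4.11 requires root-cause analysis only where a use error, close call or use difficulty is present. A deviation that falls outside those categories could therefore also go uninvestigated.

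**Working it through.** The protocol states no figure on this point, so there is nothing to reproduce. The check applies each rule to one hypothetical event.

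**Event.** A self-testing adult makes 5 circles in a nostril instead of 10, does not go back, shows no frustration, asks for no help, and later sees a valid negative strip. I assume that an uninfected person's strip would read negative with either number of circles.

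| Rule | Applies? | Reason |
|---|---|---|
| Table 7, step 9 criterion | Failed | 5 is fewer than 10 |
| Table 10, Success | No | The step was not done correctly |
| Table 10, Close Call | No | No retry that succeeded, and no sign of frustration or re-reading |
| Table 10, N/A | No | The cause was within the participant's control |
| Table 10, Use Error: inability or assistance bullets | Not clearly | The participant moved on unaided; whether a short count is an inability is left open |
| Table 10, Use Error: IFU-deviation bullet | No | The strip responded as intended and expected |
| Table 10, Use Error: lead sentence | Unclear | Depends on whether the result meant is that of the step or of the test |
| Table 10, Use Difficulty | Not necessarily | An unnoticed short count need not show as difficulty, and the flag does not replace a score |

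The same reasoning holds for rotating the swab in the tube for 3 seconds instead of 15 (step 10).

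**Do other parts of the protocol settle it?**

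- Section 4.4 ties the task criteria to success and use error, but it points to section 4.1.1 and Appendix 6. The table is in 4.4.1 and the discussion guide is headed Appendix 10.
- Section 4.5 has no equivalent sentence. It covers the two caregiver groups, 15 + 15 = 30 of the 60 testers.
- Section 4.10 sends the reader to Table 4 for the scoring definitions. Table 4 is the sample-size table; the definitions are in Table 10.
- The guide's scoring grids (6.3.1 and 6.4) have a Use Error box on each row, but the rows reprint the IFU instruction and not the acceptance criterion.
- Guide section 6.7 scores the strip reading on interpretation alone, so a correctly read negative is a success whatever the sample quality.

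**Scope.** Steps 8, 9, 10 and 11 are 4 of the 14 numbered steps. With 60 testers that is 4 × 60 = 240 step scores in which the ambiguity can arise. It is not a count of misclassified scores, which would require knowing how often testers deviate.

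**The case against.** A reader might infer that Table 10 counts an IFU departure as a use error only when the device responds unexpectedly, and hence that the study cannot register sampling errors. The protocol does not support that.

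- The three bullets are introduced as examples, so the list is open. Two of them, inability and assistance, need no device response.
- The lead sentence speaks of a result, not of the strip. Because scoring is by task, it can be read as the result of the step.
- The Close Call row itself uses the term use error for acting without accurate reference to the IFU, with no strip outcome involved.
- Section 4.4 names the task criteria as success/use-error criteria, and the guide lets the moderator tick Use Error for every swabbing and extraction row before the strip is read.
- The analysis also draws on video and expert review.

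All of this stands. A careful rater can record short swabbing as a use error, and many would. It does not remove the gap: section 4.11 names Table 10 as the governing rule, Table 10 never says that failing an acceptance criterion is a use error, and its one bullet on IFU departures points the other way.

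A reader might also try to size the problem from the share of infected testers. The protocol gives no prevalence, and such a figure would presuppose the strict reading rejected above, so none is offered.

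The reference to packaging is a minor misfit. Section 2.3 excludes only the outer packaging, while the foil and the swab wrapper are handled in tested steps. The phrase is too narrow for a definition that must cover the whole kit and IFU.

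**Conclusion.** The point holds as a conflict between two scoring rules. Table 10 defines a use error by what it leads to, and Tables 7 and 8 judge what the tester was seen to do. An uncorrected deviation in steps 8 to 11 that ends in an ordinary negative strip fails its step criterion but has no clear Table 10 category. Scores could differ between raters, and the event could miss the root-cause trigger.

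The conclusion rests on the protocol wording and on one assumption, that a poor swab from an uninfected person still reads negative. The exposure is 240 step scores; the number actually affected is unknown. This is worth correcting because task performance is the main evidence for the study's objective. It does not show that sampling errors would go unrecorded.

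**What to change.** 1. In section 4.11 and in the Use Error row of Table 10, state: *An acceptance criterion in Table 7 or Table 8 that is left unmet without successful self-correction, or is met only with assistance from study personnel, is a Use Error whatever the strip shows.* Keep the inability and assistance bullets, so that a tester who was helped to meet a criterion is not scored a success under one rule and an error under another.
2. In the lead sentence of the Use Error row, replace the reference to using the packaging with *while using the test kit or IFU*.
3. Correct the pointers: section 4.4 to section 4.4.1 and to the guide's actual appendix number, and section 4.10 to Table 10.
4. Before applying the rule, reconcile two steps; otherwise testers who follow one text would be scored as errors under another. In Table 7, step 9 instructs one nostril while its criterion requires both. Step 5 (nose-blowing) is carried over for caregivers by Table 8, while the guide marks it as not required when the test is on someone else. Which version is right is for the sponsor to settle.

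The cost is a few lines of protocol text and a short briefing for moderators and observers. The downside is that reported use-error counts may be higher.
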